Appendix 1b

Schedule of Activities for Patients who were Eligible for the GENERATION-HD1 Study but not Randomized due to Logistical Challenges Resulting from the COVID-19 Pandemic (cont.)

- ^j A neurologic examination (including fundoscopy), performed at every clinical visit, should include assessment of mental status, level of consciousness, cranial nerve function, motor function, sensory function, reflexes, gait, and coordination. The neurologic examinations should be conducted in the same manner on each occasion to ensure comparability to previous examinations. Neurologic examinations should be performed before and after treatment on each dosing day, *or before the lumbar puncture, if there is no study treatment administration*. Weight should also be measured at each visit. Any abnormality identified at screening and baseline (inclusion visit) should be recorded on the General Medical History and Baseline Conditions eCRF. Changes from baseline abnormalities should be recorded in patient notes. New or worsened clinically significant abnormalities (i.e., beyond expected variation, normal age-related change or HD-related clinical progression) should be recorded as adverse events on the Adverse Event eCRF.
- ^k Electrocardiograms should be triplicate at screening and subsequent ECGs should be a single ECG performed after the patient has been resting in a supine position for at least 10 minutes. Lead placement should be as consistent as possible. Electrocardiograms for each patient should be obtained from the same machine whenever possible. All ECGs are to be obtained prior to other invasive procedures scheduled at that same time (e.g., blood draws) and should not be obtained within 30 minutes after any meal.
- ^l Hematology includes WBC count, RBC count, platelet count, hemoglobin, hematocrit, differential count (neutrophils, eosinophils, basophils, monocytes, lymphocytes).
- ^m Serum chemistry panel: includes bicarbonate or total carbon dioxide (if considered standard of care for the region), sodium, potassium, chloride, glucose, BUN or urea, creatinine, total protein, albumin, phosphorus, calcium, total and direct bilirubin, ALP, ALT, AST, uric acid, gamma-glutamyl transferase, and CPK.
- ⁿ All women of childbearing potential will have a serum pregnancy test at screening. Urine pregnancy tests will be performed at specified subsequent visits. If a urine pregnancy test is positive, it must be confirmed by a serum pregnancy test.
- ^o Urinalysis includes dipstick (pH, specific gravity, glucose, protein, ketones, blood) and microscopic examination for all abnormal dipstick results (sediment, RBCs, WBCs, casts, crystals, epithelial cells, bacteria).
- ^p Pharmacokinetics and immunogenicity samples will be collected prior to dosing. *PK plasma samples are not required to be collected after the study treatment is paused. Immunogenicity plasma samples will continue to be collected.*
- ^q Magnetic resonance imaging should take place as early as possible within the screening window but may take place at any time during screening. The MRI safety and efficacy screening scan will need to pass the central laboratory image quality control check and the results must be available before the patient can be enrolled in the study. Magnetic resonance imaging must be scheduled to occur before the LP. The follow-up MRI scan should be performed 7–14 days prior to the LP to allow time for re-scanning if the quality of the initial MRI is inadequate. If the re-scan cannot be performed prior to the LP, then it can be conducted the day after the LP, as long as there are no post-LP contraindications and it occurs within 2 weeks of the original scan.

Appendix 1b

Schedule of Activities for Patients who were Eligible for the GENERATION-HD1 Study but not Randomized due to Logistical Challenges Resulting from the COVID-19 Pandemic (cont.)

- ^r The C-SSRS will be used to assess eligibility for the study (full version at screening, requiring approximately 20 minutes to administer) and to monitor the patients throughout the study at clinic visits (follow-up version, requiring approximately 5 minutes to administer, assuming absence of suicidal ideation and no change in clinical status from previous administration). *C-SSRS will continue to be performed as per the original schedule even if the study drug administration is paused.*
- ^s The cUHDRS is a composite motor, cognitive, and global functional clinical outcome measure in patients with HD comprised of the TFC, the TMS, the SDMT, and the SWR scores.
- ^t The electronic devices for remote data collection will be supplied to patients at screening and must be returned to the clinic in cases where the patient does not meet eligibility criteria, at the end of the study, or upon early termination from the study.
- ^u *While study dosing is paused, the CSF sample for safety/biomarkers and local PT and/or INR, aPTT and Platelet count will be collected every 16 weeks for all patients. Details about the lumbar puncture schedule are addressed in [Appendix 2b](#). CSF sample for PK analysis is not required after the treatment is paused. Within 72 hours prior to performing each scheduled LP, local laboratory analysis of coagulation factors (INR and/or PT, aPTT) and platelets must be conducted and the results reviewed. Collection for these local laboratory tests may occur at any time in the 72 hours prior to the LP. The LP should be performed at approximately the same time at each visit (ideally in the morning between 8:00 a.m. and 12:00 p.m. or in the early afternoon between 12:00 p.m. and 3:00 p.m.) to minimize potential diurnal variation of CSF parameters. Cerebrospinal fluid (20 mL) is to be collected for analyses using a LP collection kit. If there are difficulties in collecting 20 mL of CSF, a minimum of 5 mL should be collected over a maximum of 60 minutes, once CSF flow has been established. If only 5 mL is collected after 60 minutes, the operator must confirm CSF flow is present prior to injecting drug at 60 minutes. A 24G atraumatic needle, as specified in the LP procedure and CSF collection guidelines, should be used. Depending on institutional guidelines, local anesthesia should be used for the procedure. Sedation may not be used. Spinal ultrasound may be used for the LP procedure if deemed necessary, but is not required. Ultrasound guidance may be used if attempts at LP without imaging are unsuccessful, if it is local practice to use ultrasound, or if institutional guidelines dictate use of ultrasound with each LP. Fluoroscopy guidance can also be used, if local institutional guidelines dictate and local IRB/ECs and HAs have approved the use of the technique, but it is not required. Where fluoroscopy is used, patients should also be informed and consent obtained. Patients will be discouraged from resting supine after the LP procedure and will be encouraged to mobilize immediately by walking around at a minimum and, if feasible, walking briskly for approximately 30 minutes. Patients should not perform any activity that is associated with a change in the ambient air pressure for at least 24 hours *post LP procedure* (e.g., air travel, scuba diving, or hot air balloons). In case of a failed IT bolus dosing procedure (e.g., due to an inadequate establishment of access to the IT space), a second dosing attempt may occur up to 7 days after the originally scheduled dosing attempt. For this additional visit, safety and tolerability evaluations on the day of LP administration will be performed as detailed in [Appendix 1b](#), including neurological examination (predose and postdose), vital signs, and a review of adverse events and concomitant medication. If the second dosing attempt occurs more than 72 hours after the last coagulation panel and platelets test, local laboratory analysis of coagulation factors (INR and/or PT, aPTT) and platelets need to be conducted again and results reviewed prior to the LP attempt.*

Appendix 1b

Schedule of Activities for Patients who were Eligible for the GENERATION-HD1 Study but not Randomized due to Logistical Challenges Resulting from the COVID-19 Pandemic (cont.)

- ^v Excluding MRIs, which have a visit window of –14 to –7 days.
- ^w The EQ-5D-5L will only be completed in-clinic at each study drug administration visit. *The EQ-5D-5L will continue to be performed as per the original schedule even if the study drug administration is paused.*
- ^x Telephone safety follow-up will be conducted Q8W (alternating with in-clinic visits) for 1 year for all patients, and then Q16W in between study administration visits for Q16W arm to check for any change in patient status (e.g., adverse events and concomitant medications) since their last visit and depending on patient's health status. An unscheduled clinic visit may be arranged, if needed. If a patient is due for a telephone safety call and they are in-clinic then this telephone safety follow-up call can be completed in-clinic at the site's discretion. As a result of the COVID-19 pandemic, only where sites are impacted, these telephone safety calls can be conducted instead of an in-clinic visit.
- ^y Medication (e.g., prescription drugs, over-the-counter drugs, vaccines, herbal or homeopathic remedies, nutritional supplements) used by a patient in addition to protocol-mandated treatment from the time of entry into Study BN40955 to the study completion/discontinuation visit.
- ^z After informed consent has been obtained but prior to initiation of study drug, only serious adverse events caused by a protocol-mandated intervention should be reported. After initiation of study drug at baseline (inclusion visit), all adverse events will be reported until 5 months after the final dose of study drug. After this period, all deaths, regardless of cause, should be reported. In addition, the Sponsor should be notified if the investigator becomes aware of any serious adverse event that is believed to be related to prior study drug treatment.
- ^{aa} Safety follow-up visit occurs +20 weeks after EoT.
- ^{bb} The DCL will be assessed at screening only (i.e., without the full TMS assessment). The TMS scale will be assessed (excluding the DCL) at all other timepoints.
- ^{cc} *Effective 22 March 2021, Q8W and Q16W study drug administration is immediately paused.*

Appendix 2a Visit Schedule for the First 2 Years of Treatment

Month	0	1	2	3	4	5	6	7	8	9	10	11	12	13	14	15	16	17	18	19	20	21	22	23	24
Week	1	5	9	13	17	21	25	29	33	37	41	45	49	53	57	61	65	69	73	77	81	85	89	93	97
Q8W study drug administration ^a	x	P	x	P	x	P	x	P	x	P	x	P	x		x		x		x		x		x		x ^b
Q16W study drug administration ^a	x	P	CV	P	x	P	CV	P	x	P	CV	P	x		P		x		P		x		P		x ^c
Efficacy assessments	x				x				x				x				x				x				x ^d

CV=non-treatment clinic visit; P=phone call; Q8W=every 8 weeks; Q16W=every 16 weeks.

Notes: The non-treatment clinic visit includes collection of the following assessments during the first year of assignment to Q16W regimen: vital signs, neurologic examination, hematology, chemistry, pregnancy test, urinalysis, concomitant medications, and adverse events.

^a Q8W and Q16W study drug administration should be immediately paused until further assessments can be conducted following the release of the USM- DIL on March 22, 2021

^b Patients will continue Q8W dosing until end-of-treatment.

^c Patients will continue alternating telephone safety follow-up and treatment visits until end-of-treatment.

^d Patients will continue efficacy assessments Q16W throughout treatment period.

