6.5 SAFETY ANALYSES

The safety analysis population will consist of all randomized patients who received at least one dose of study drug, with patients grouped according to treatment received.

All verbatim AE terms will be mapped to Medical Dictionary for Regulatory Activities (MedDRA) thesaurus terms. The Adverse Event Severity Grading Scale (see Section 5.3.3) will be used for assessing AE severity. Laboratory values determined as an AE should be graded as per [Appendix 10](#), which is based on the NCI CTCAE (v5.0).

All safety data, including AEs, laboratory tests, neurologic examination, C-SSRS, MoCA, ECG, and vital signs, will be reported in individual listings and summarized by treatment for each assessment time using descriptive statistics. For continuous variables, both the original value as well as the change from baseline will be reported.

The incidence of AEs will be summarized on the basis of body systems and dictionary preferred terms. The incidence of AEs by severity and relationship to study drug or study procedure and incidence of marked abnormal laboratory test results will be provided.

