Appendix 1a Schedule of Activities for All Patients Except Those Undergoing Screening

	Inclusion Visit ^a	Treatment Period ^b	EoT ^c	SFU ^d
Week	Last applicable visit of preceding study ^a	Treatment and Assessment Frequency	+4 weeks	+20 weeks
Day (Window)		±1 week ^e	±1 week	±1 week
Signed informed consent ^f	x			
Review of inclusion and exclusion criteria	x			
Demographic data	x			
Medical history and baseline conditions ^g	x			
Vital signs ^h	x ⁱ	At each clinic visit	x	x
Complete physical examination ^j	x ⁱ	Q32W	x	x
Neurologic examination ^l	x ⁱ	At each clinic visit (see Appendix 12)	x	x
ECG ^m	x ⁱ	Q32W	x	x
Hematology ⁿ	x ⁱ	At each clinic visit	x	x
Chemistry ^o	x ⁱ		x	x
Pregnancy test ^p	x ⁱ		x	x
Urinalysis ^q	x ⁱ		x	x
Local PT and/or INR, aPTT, platelet count ^s	x ⁱ	At each study drug administration visit	x	x

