Appendix 1a
Schedule of Activities for All Patients Except Those Undergoing Screening (cont.)

	Inclusion Visit ^a	Treatment Period ^b	EoT ^c	SFU ^d
Week	Last applicable visit of preceding study ^a	Treatment and Assessment Frequency	+4 weeks	+20 weeks
Day (Window)		±1 week ^e	±1 week	±1 week
Plasma sampling for PK ^r	x ⁱ	Q16W for 48 weeks and then Q32W thereafter		
Plasma sampling for immunogenicity testing ^r	x ⁱ		x	x
Plasma samples for biomarkers	x ⁱ		x	x
CSF sample for PK/safety/biomarkers ^s	x ⁱ	At each study drug administration	x	
MoCA	x ⁱ	Q16W	x	
C-SSRS ^t	x ⁱ	At each study drug administration	x	
Mandatory Structural MRI ^u	x ⁱ	Q32W ^k	x	
Optional resting-state functional MRI and diffusion-weighted MRI / NODDI ^u	x ⁱ	Q32W ^k	x	
Optional MRI brain and spine with contrast media for patients from Study BN40697 ^v	x	Q32W	x	

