- ^t *The C-SSRS will be used to monitor the patients throughout the study at clinic visits (follow-up version, requiring approximately 5 minutes to administer, assuming absence of suicidal ideation and no change in clinical status from previous administration). C-SSRS will continue to be performed as per the original schedule even if the study drug administration is paused.*

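### Section 6.5 tabulates the incidence of marked laboratory abnormalities by arm without allowing for more testing in Q8W (to Week 97: CSF 12 vs 6, central laboratory tests 12 vs 9)

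*Combined protocol and SAP*

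**What the plan says.** Section 6.5, which the synopsis labels the primary analysis, groups patients by treatment received. It plans descriptive summaries at each assessment time, AE incidence tables, and one further output: "incidence of marked abnormal laboratory test results will be provided". It does not mention a common set of visits, a rate per test, or the number of tests performed.

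The schedule sets how often each arm is tested:

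- Haematology, chemistry, urinalysis and the neurologic examination are done "At each clinic visit" (Appendix 1a).
- CSF, which Section 4.5.6 lists among the laboratory safety tests, is taken "At each study drug administration" (Appendix 1a). Local coagulation and platelets follow the same visits.
- In the Q16W arm, Appendix 2a adds clinic visits without dosing at Weeks 9, 25 and 41. Their content is introduced by "The non-treatment clinic visit includes collection of the following assessments during the first year of assignment to Q16W regimen". The list covers the central laboratory tests and a neurologic examination, but not CSF or local coagulation.
- After year 1 the Q16W mid-interval contact is a telephone call: "Patients will continue alternating telephone safety follow-up and treatment visits until end-of-treatment". For the other arm, "Patients will continue Q8W dosing until end-of-treatment".
- During the pause (Appendix 1a footnote s, Appendix 2b), CSF and local coagulation/platelets are collected every 16 weeks in both arms. Q8W patients keep their intermediate clinic visits, without lumbar puncture; Q16W patients have telephone calls after year 1.

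**The concern.** Incidence is normally read as the share of patients with at least one abnormal result during follow-up. For a transient abnormality that share rises with the number of tests, even if each test carries the same risk. An arm tested more often therefore shows a higher incidence for reasons unrelated to the drug.

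Here the extra testing falls on Q8W, the same direction as the harm the plan has in mind: Section 3.3.1 justifies Q16W partly as a way to reduce possible complications of more frequent intrathecal dosing. Section 4.2 also foresees that one regimen may be selected for the programme. A difference produced by the schedule could be read as toxicity of more frequent dosing.

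**Working it through.** **Inputs.** Visit codes come from the Appendix 2a and 2b grids ("CV=non-treatment clinic visit; P=phone call; Q8W=every 8 weeks; Q16W=every 16 weeks") and test frequencies from Appendix 1a. The documents give no per-test risk, no within-patient correlation and no expected incidence, so there is no planned figure to reproduce. Risk and correlation below are assumptions shown over a range.

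**Step 1: scheduled assessments after baseline, Q8W vs Q16W.** Q8W dosing visits are Weeks 9 to 97 in steps of 8 (12 visits). Q16W dosing visits are Weeks 17 to 97 in steps of 16 (6 visits), plus non-dosing clinic visits at Weeks 9, 25 and 41.

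| Assessment | Weeks 2–49 | Weeks 50–97 | Weeks 2–97 |
|---|---|---|---|
| CSF safety, local coagulation/platelets, dosing | 6 vs 3 | 6 vs 3 | 12 vs 6 |
| The same, pause | 3 vs 3 | 3 vs 3 | 6 vs 6 |
| Haematology, chemistry, urinalysis, dosing or pause | 6 vs 6 | 6 vs 3 | 12 vs 9 |
| Neurologic examinations, dosing (pre- and postdose) | 12 vs 9 | 12 vs 6 | 24 vs 15 |
| Neurologic examinations, pause | 6 vs 6 | 6 vs 3 | 12 vs 9 |
| AE contacts, clinic or telephone | 12 vs 12 | 6 vs 6 | 18 vs 18 |

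**Step 2: chance of at least one abnormal result, same risk p per test in both arms, independent tests.** P(any) = 1 − (1 − p)^k for k tests.

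| p | k = 12 | k = 9 | k = 6 | Ratio 12 vs 6 | Ratio 12 vs 9 |
|---|---|---|---|---|---|
| 1% | 11.4% | 8.6% | 5.9% | 1.94 | 1.31 |
| 2% | 21.5% | 16.6% | 11.4% | 1.89 | 1.29 |
| 5% | 46.0% | 37.0% | 26.5% | 1.74 | 1.24 |

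For central laboratory tests in Weeks 50–97 alone (6 vs 3), p = 2% gives 11.4% vs 5.9%, ratio 1.94. In year 1 (6 vs 6) the ratio is 1.00.

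**Step 3: within-patient correlation ρ (beta-binomial), p = 2%.** With a = p(1 − ρ)/ρ and b = (1 − p)(1 − ρ)/ρ, P(any) = 1 − B(a, b + k)/B(a, b), where B is the beta function. Ratios use unrounded values.

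| ρ | k = 12 | k = 9 | k = 6 | Ratio 12 vs 6 | Ratio 12 vs 9 |
|---|---|---|---|---|---|
| 0.2 | 11.3% | 9.7% | 7.7% | 1.46 | 1.16 |
| 0.5 | 6.0% | 5.5% | 4.8% | 1.26 | 1.09 |
| 0.9 | 2.6% | 2.6% | 2.5% | 1.06 | 1.03 |

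**Step 4: common visits only.** Central laboratory tests become 9 vs 9 (Weeks 9, 17, 25, 33, 41, 49, 65, 81, 97) and CSF 6 vs 6 (Weeks 17, 33, 49, 65, 81, 97). At p = 2% with independent tests this is 16.6% in both arms and 11.4% in both arms. The ratio is 1.00 at any p.

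**The case against.** The plan already does part of the balancing. The extra Q16W visits make central laboratory testing and neurologic clinic visits equal in year 1, and the pause makes CSF and local coagulation equal. The study is descriptive, with no powered comparison, and Table 1 assigns many patients by their previous regimen, so equal testing would not by itself make the full arms comparable. AE enquiry is balanced at 18 contacts each. The size of the effect rests on assumed inputs.

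All of this stands, and it limits the point. It does not answer it: an incidence table by arm invites a side-by-side reading, and central laboratory testing stays at 2:1 after year 1, with or without dosing, in a study where participation may last about 6 years.

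A reader might infer more: that laboratory tests, CSF, neurologic examinations and C-SSRS are all done twice as often in Q8W, and that an any-abnormal incidence is inflated for each. The documents do not support that.

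- Over Weeks 2–97 the central laboratory ratio is 12/9 = 1.33, not 2.
- Section 6.5 plans neurologic examination and C-SSRS as listings and summaries at each assessment time, and a visit-specific summary is not inflated by having more visits.
- Neurologic findings are exposed only indirectly. Section 4.5.3 sends new or worsened clinically significant findings to the AE form, and a telephone call cannot find a sign that needs examination. This matters mainly after Week 49.
- For C-SSRS, the Appendix 1a table and Appendix 3 tie it to dosing visits, while footnote t to Appendix 1a refers to clinic visits generally. The same footnote adds "C-SSRS will continue to be performed as per the original schedule even if the study drug administration is paused", which leaves open which schedule is meant. No inflation claim can rest on it.

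**Conclusion.** The point holds for laboratory incidence. At equal per-test risk, the Section 6.5 output would show more patients with marked abnormalities in Q8W than in Q16W. This applies to CSF and local coagulation/platelets while dosing, and to central laboratory tests after Week 49. At an assumed 2% per test, the ratio for 12 vs 6 tests is 1.89 if independent and 1.26 at ρ = 0.5; for 12 vs 9 it is 1.29 and 1.09. It approaches 1 for persistent abnormalities.

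This rests on three assumptions: incidence means at least one abnormal result per patient, CSF results enter that table, and follow-up reaches Week 97. A patient paused earlier has a cumulative CSF ratio somewhere between 1 and 2. The point does not show that any Q8W excess already reported in Section 5.1 is an artefact. It is an inexpensive improvement to the safety tables, not a flaw in the design.

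**What to change.** Add to Section 6.5 or the SAP:

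- Base the Q8W vs Q16W incidence of marked laboratory abnormalities on visits at which that test is scheduled in both arms. For central laboratory tests these are Weeks 9, 17, 25, 33, 41 and 49, then every 16 weeks. For CSF and local coagulation/platelets they are Weeks 17, 33 and 49, then every 16 weeks.
- If new neurologic findings are compared as incidence, use the central laboratory weeks and the pre-dose (or only) examination. At Weeks 9, 25 and 41 while dosing, Q8W has a postdose examination and Q16W does not.
- Report the number of assessments performed per arm beside each incidence.
- Keep every visit in the listings and in within-arm incidence.
- Separately, reconcile the C-SSRS timing in footnote t with the Appendix 1a table and Appendix 3.

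The cost is a few sentences and minor programming, with no change to patient procedures. The downside is that Q8W-only visits leave the between-arm table. The change equalises the number of tests; it does not address non-random assignment.

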Appendix 2b Visit Schedule for the First 2 Years of Study Participation While on Treatment Pause

Month	0	1	2	3	4	5	6	7	8	9	10	11	12	13	14	15	16	17	18	19	20	21	22	23	24
Week	1	5	9	13	17	21	25	29	33	37	41	45	49	53	57	61	65	69	73	77	81	85	89	93	97^a
Q8W ^{b, c}	LP	P	NLP ^d	P	LP	P	NLP ^d	P	LP	P	NLP ^d	P	LP		NLP ^d		LP		NLP ^d		LP		NLP ^d		LP
Q16W ^e	LP	P	CV	P	LP	P	CV	P	LP	P	CV	P	LP		P		LP		P		LP		P		LP

CV=non-treatment clinic visit; P=phone call; Q8W=every 8 weeks; Q16W=every 16 weeks; LP=clinic visit with lumbar puncture; NLP= clinic visit without lumbar puncture

Notes: The non-treatment clinic visit includes collection of the following assessments during the first year of assignment to Q16W regimen: vital signs, neurologic examination, hematology, chemistry, pregnancy test, urinalysis, concomitant medications, and adverse events.

^a All patients should continue performing the corresponding visits as described in [Appendix 2b](#) beyond the first 2 years.

^b Q8W=patients randomized to Q8W and paused from receiving RO7234292 study drug following the USM-DIL (dated 22 March 2021).

^c Patients who were randomized to Q8W study drug administration and paused from receiving RO7234292 study drug will continue to undergo clinic visits performing LP and alternate non LP (NLP) visits. At the LP visits, CSF sample for safety/biomarkers will be performed. Local PT and/or INR, aPTT, Platelet count and neurological examinations will be performed prior to LP only. CSF sample for PK and plasma for PK will not be required after study treatment was paused. Immunogenicity samples will continue to be collected.

^d Non-LP visits will continue as described in [Appendix 1a](#) and [Appendix 1b](#). CSF samples for PK/safety/biomarkers and local PT/and/or INR, aPTT and platelet count are not required at these visits. Neurological examinations should be performed at Non-LP visits.

^e Q16W=patients randomized to Q16W and paused from receiving RO7234292 study drug following the USM-DIL (dated 22 March 2021)..

